Title of the Protocol: Use of Ulipristal Acetate in Induction of Second Trimestric Missed Abortion in Women with Previous Caesarian section: Randomized Controlled Trial.

Document date : November 2018

Background

Miscarriage is a common event in a woman's life. Approximately 20% of clinically recognized pregnancies end in a miscarriage [1]. Most miscarriages occur before 12 weeks and it has been estimated that only 2–3% of pregnancies end spontaneously in the second trimester. Second-trimester pregnancy loss has been defined as miscarriage diagnosed between the duration of gestation of 12–24 weeks [2]. According to the World Health Organization, miscarriage is defined as the premature loss of a fetus at < 22 weeks of the pregnancy and weighing < 500 g. [3]

Medical management of miscarriage and induced abortion has become the gold standard in clinical practice. However, the treatment of second trimester miscarriage has been addressed in only few research studies. In a recent systematic review of medical treatments for incomplete miscarriage, no randomized trials focused specifically on the treatment of miscarriage beyond 13 week's gestation were identified [4]. Thus the clinical practice on the treatment of late miscarriages is mainly based on the knowledge derived from studies on second trimester induced abortion. [6]

Medical abortion is the termination of pregnancy with use of medications to induce a process similar to a miscarriage. It is an alternative to aspiration curettage. Use of a combination of mifepristone (an antiprogestrone) and misoprostol (a prostaglandin) is the primary method of medication abortion used according to the American College of Obstetricians and Gynecologists. [7]

Ulipristal is a selective progesterone receptor modulator (SPRM) with primarily antiprogestin activity. Due to its antiprogestin activity it is highly effective for use in emergency contraception. Its primary mechanism of action is delay of ovulation, but endometrial effects that may affect implantation may also contribute to efficacy. [9]

A Cochrane review demonstrated that medical abortion in the second trimester (13–28 weeks) using the combination of mifepristone and misoprostol appeared to have the highest efficacy and shortest abortion time interval compared to other medical regimens. [10]

Mifepristone may be used in combination with misoprostol to decrease the induction-to-abortion interval and minimize pain. By opposing the activity of progesterone, mifepristone elicits a variety of effects that make the uterus more susceptible to abortion. These effects include cervical dilation, decidual necrosis, increased endogenous prostaglandin production, and increasing uterine sensitivity to exogenously administered prostaglandin. Mifepristone administration gradually elicits a five-fold increase in sensitivity to prostaglandin 24 to 48 hours after its administration [11]. The synergy between mifepristone and prostaglandin permits greater efficacy of prostaglandin at lower doses, potentially minimizing side effects [12].

The improved efficacy with mifepristone was best illustrated in a randomized trial that compared second-trimester abortion with misoprostol (buccal 400 mcg, then 200 mcg every six hours) preceded by either mifepristone (oral 200 mg) or placebo (oral vitamin C). Women in the mifepristone group had a significantly shorter median procedure time (10 versus 18 hours). In addition, the mifepristone group had a non significant association with lower rates of retained placenta (3.1

versus 6.3 percent) and analgesic requirements (27.2 versus 39.3 mg morphine). Side effects were similar between groups. [13].

What is already known on this subject? AND What does this study add?

Ulipristal acetate (UPA) is a selective progesterone receptor modulator approved for use as an emergency contraceptive and for preoperative treatment of uterine fibroids. It has not been used as an abortifacient drug in previous studies. However, due to its antiprogestin activity, like its family member Mifepristone, it could be effective if it is used alongside Misoprostol according to FIGO guidelines for induction of abortion. This may decrease the time taken for patients to abort, may increase the success rate of having a complete abortion thus decreasing the need for aspiration & hysterotomy. All this, would lead to less morbidity, shorter hospital admission stay, better psychological wellbeing for patients and a decrease in all hospital costs

The aim of this work is to assess the effectiveness and safety of Ulipristal Acetate in the management of 2nd trimester missed abortion along with misoprostol in pregnant women with previous caesarean section versus the use of misoprostol only with placebo as regards the time needed for abortion.

Research Question

In pregnant women with 2nd trimester missed abortion with previous caesarean section , does Ulipristal Acetate decrease the time interval to achieve abortion when combined with Misoprostol in comparison to Misoprostol alone?

Hypothesis

In pregnant women with 2nd trimester missed abortion with previous caesarean section , Ulipristal Acetate may decrease the time interval to achieve abortion when combined with Misoprostol in comparison to misoprostol alone.

Study Design

Type of Study: A Randomized Controlled Trial.

Study Setting: Ain Shams University Maternity Hospital.

Study Period: Starting from January 2019 to January 2020.

Participants

Study Population: Women with 2nd trimester missed abortion with previous caesarean section undergoing medication abortion attending either outpatient clinic or emergency room

Eligibility Criteria:

Inclusion Criteria:

- Women with 2nd trimester missed abortions
- Gestational age 13-26 weeks.
- Women with a previous caesarian section scar,(Para-1CS till Para-4CS).
- Women counseled and chose medication abortion rather than surgical evacuation

Exclusion Criteria:

- Women with an accompanying medical disorder such as: Preeclampsia, DM or Heart disease.
- Primigravida women or non scarred uterus.
- Women with previous myomectomy or hysterotomy scar or upper segment caesarean section scar.

- Induction of abortion in women with congenital fetal malformations or positive fetal pulsations due to medical disorder
- Women with placenta previa.
- Allergy or contraindications to either Ulipristal acetate or Misoprostol.
- Women with inevitable abortion in the form of vaginal bleeding or uterine contractions.

All women who met the inclusion criteria will be assessed.

This assessment will include:

Detailed History:

Personal history (Maternal age, weight, height).

Obstetric history . Gravidity, Parity, previous operative delivery.

Any associated complication during pregnancy.

Menstrual history (Last menstrual period).

Maternal medical history (Hypertension & Coagulopathies).

Physical Examination:

- General examination:** a. Vital signs b. Chest and heart examination
- Abdominal examination:** a. Gestational age b. Fetal weight, amount of liquor, fetal lie and presentation, fetal heart sounds c. Uterine contractions and scar of previous surgeries
- Vaginal examination** to detect cervical dilatation, consistency, position and length.

Investigations:

CBC, Liver Function, Kidney function, Random blood sugar, Prothrombin time (PT)

Obstetric ultrasound study: For assessment of gestational age, fetal life, implantation site of the placenta and fetal weight.

Interventions

The study sample, will be divided into two groups as follows:

Group A: will receive Ulipristal acetate 30mg, starting misoprostol 12 hours later 100µg every 6 hours buccal according to FIGO guidelines 2017.

Group B: will receive placebo tablet then 12 hours later start misoprostol 100µg every 6 hours buccal according to FIGO guidelines 2017.

Then women in both groups will have rest for 24hours after 5 doses of misoprostol

and restart misoprostol-only in both groups with the same above regimens, repeating the same sequence for two weeks unless there is excessive bleeding or infection. If failed, patient will proceed to hysterotomy.

Primary outcome

1. Induction-to-abortion interval time.

Secondary outcome

1. Success rate for complete evacuation between both groups.
2. Occurrence of side effects: i) Nausea ii) Vomiting iii) Fever iv) Pain, between both groups.
3. Rate of uterine rupture between both groups.

4. Amount of blood loss, as a comparison between both groups.
5. Rate of hysterotomy between both groups.

Sampling Method:

Sample Size: A pilot sample was used primarily, to accurately calculate the main study sample. According to Julious SA. ⁽⁶⁾, a pilot sample size of 24 (12 per arm) was used. The objective is not to prove superiority of the treatment but to test trial procedures and processes and to get estimates of parameters for the main trial sample size calculation. Women fulfilling the inclusion criteria and consenting were randomly assigned to either group

Randomization, Allocation and Concealment:

A computer generated list via MedCalc® Software, version 13.2.2 will be used for randomization, assigning each participant number to either study group using sequentially numbered, otherwise identical, sealed envelopes (SNOSE), each

containing a 2-inch by 2-inch paper with a written code designating the assigned group. These papers were placed in a folded sheet of aluminum foil fitted inside the envelope. To ensure concealment, efforts will be taken to assure absence of any detectable differences in size or weight between intervention and control envelopes. Envelopes will be chosen to be opaque and lined inside with carbon paper. Envelopes will be opened sequentially after writing the subject's tracking information on the envelope so that the carbon paper served as an audit trail. At the time of procedure, the

responsible investigator will open the envelope to reveal the assignment, and she will introduce the planned method.

After enrollment, the cases will be randomly allocated into two groups:

- **Group A(n=30):** Will be the case group, it includes cases who will receive Ulipristal Acetate plus Misoprostol.
- **Group B(n=30):** will be the control group, it includes cases who will receive Misoprostol only plus a structurally similar placebo drug manufactured at Ain Shams Pharmacology department.

Ethical Considerations:

The nature and scope of the clinical study will be explained in a form understandable to the patient and an informed consent document, in Arabic language, contains all locally required elements and specifies who informed the patient, will be provided and the patient must give written consent. Patients should be counseled that medication abortion takes longer and that they may have a greater awareness of blood loss and passage of pregnancy tissue with high risk of rupture uterus (0.3%)[16] and blood transfusion. The study protocol and patient informed consent will be reviewed and approved by the Ethics Committee of the Obstetrics and Gynecology Department Ain Shams University.

1. **NICE Clinical guideline 2012. Diagnosis and initial management in early pregnancy of ectopic pregnancy and miscarriage.**
2. **McNamee KM, Dawood F, Farquharson RG. Mid-trimester pregnancy loss.**
Obstet Gynecol Clinics North America 2014; 41(1):87–102.

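### Infection, transfusion and early stops for bleeding or infection are not outcomes, and hysterotomy is counted without its reason, although safety is part of the aim

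*Protocol*

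**What the plan says.** The closing paragraph of the protocol's section on what is already known makes safety part of the aim, alongside effectiveness. The same section says ulipristal has not been studied as an abortifacient before. The eligibility criteria admit women with one to four previous caesarean sections.

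Three parts of the protocol bear on harm:

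- **Interventions.** Misoprostol continues by "repeating the same sequence for two weeks unless there is excessive bleeding or infection. If failed, patient will proceed to hysterotomy". Neither the two stopping events nor failure is defined.
- **Ethical Considerations.** Women are counselled about pregnancy loss "with high risk of rupture uterus (0.3%)[16] and blood transfusion".
- **Secondary outcome.** There are five: complete evacuation; "Occurrence of side effects: i) Nausea ii) Vomiting iii) Fever iv) Pain, between both groups"; uterine rupture; amount of blood loss; and "Rate of hysterotomy between both groups".

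The SAP is one paragraph. It gives generic tests for quantitative data (t-test or Mann-Whitney) and qualitative data (chi-square or Fisher's exact), plus a log-rank test for abortion rate. It names no safety outcome.

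**The concern.** The protocol treats excessive bleeding and infection as serious enough to interrupt treatment, and transfusion as serious enough to mention at consent. None of these would be tabulated by arm if the plan were followed as written. A reader of the results could not tell how many women in each arm were infected, transfused, or taken off induction.

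The hysterotomy rate raises a related problem. A hysterotomy after two weeks of unsuccessful induction is an efficacy failure; one done for a complication is a harm. If both enter one rate, a benefit on the first and an excess of the second could offset each other.

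The reason for stopping also matters for efficacy. A woman stopped early has no ordinary induction-to-abortion interval, and the log-rank comparison is hard to interpret without knowing why she left.

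**Working it through.** **1. Match events to outcomes.**

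| Event | Where the protocol raises it | Compared between arms? |
|---|---|---|
| Uterine rupture | Ethical Considerations | Yes, secondary outcome 3 |
| Excessive bleeding, as an event | Interventions (stops treatment) | No; only the amount of blood loss, outcome 4 |
| Infection | Interventions (stops treatment) | No; only fever, within outcome 2 |
| Transfusion | Ethical Considerations | No |
| Early stop for bleeding or infection | Interventions | No |
| Hysterotomy | Interventions | Yes, outcome 5, as one rate without reason |

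**2. Can the listed outcomes stand in for the missing ones?** Fever is listed as a side effect beside nausea, vomiting and pain, while infection ends treatment, so the plan itself separates them. Blood loss is an amount with no measurement method or threshold. A t-test or Mann-Whitney test on it does not report how many women bled enough to be stopped or transfused.

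**3. How much can rupture contribute?** Inputs: 0.3% (Ethical Considerations) and 30 per arm (Randomization, Allocation and Concealment).

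- Expected ruptures: 60 × 0.003 = 0.18.
- Chance of at least one in 60: 1 − 0.997^60 = 16.5%; in one arm of 30: 1 − 0.997^30 = 8.6%.
- With 0 of 30, the upper one-sided 95% limit is 1 − 0.05^(1/30) = 9.5%.

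The documents give no rates for infection or transfusion. Under assumed rates of 1%, 3%, 5% and 10%, the chance of at least one event in 60 women is 45%, 84%, 95% and over 99%. Unless these events are nearly as rare as rupture, they are more likely to be seen than rupture is.

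**4. The hysterotomy rate.** Invented counts, for illustration only: ulipristal arm, 1 for failed induction plus 3 for a complication; control arm, 4 plus 0. Both give 4/30 = 13.3%. This applies only if surgery for a complication is counted in outcome 5, which the protocol neither states nor excludes.

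**5. What could be inferred after the change?** For 0 of 30 versus k of 30, two-sided Fisher p = 2 × C(30,k)/C(60,k):

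- k = 3: 2 × 4,060/34,220 = 0.24
- k = 5: 0.052
- k = 6: 0.024

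For two proportions at two-sided 0.05, power = Φ{[|p1 − p2|√n − 1.96√(2p̄(1 − p̄))] / √(p1(1 − p1) + p2(1 − p2))}. With assumed rates and n = 30:

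- 5% versus 15%: power 25%
- 5% versus 20%: (0.822 − 0.917)/0.456 = −0.209, power 42%

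For 80% power these contrasts need 141 and 76 per arm. The stated 30 per arm cannot be reproduced, because no effect size, SD or power is given, but this point does not depend on it.

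**The case against.** A reader might infer that the most serious expected harms are not compared between arms. The documents do not support that. Rupture, the only harm given a rate and described as high risk, is a between-arm outcome, as are amount of blood loss and total hysterotomy. That rupture is too rare to be informative in 60 women is a limit of sample size, not an omission.

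Other points on the plan's side also stand:

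- The protocol does not say that women stopped for bleeding or infection go to hysterotomy. Mixing of reasons is possible because failure is undefined; it is not stated.
- In the illustration, a rupture would still appear under outcome 3, and bleeding would enter outcome 4 as an amount. The surgery most likely to be hidden is that for infection, and fever would partly reflect it.
- Aspiration might look like another gap, since the rationale expects more complete abortions, "thus decreasing the need for aspiration & hysterotomy". It is largely covered by the complete-evacuation outcome.
- Reasons to stop treatment, consent risks and outcomes serve different purposes. That the lists differ is not a contradiction, and nothing here asks for the stopping reasons to change.
- Added counts would seldom reach significance at this size.

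None of this supplies the missing counts. Low power limits inference; it does not remove the need to report events that the protocol itself treats as ending treatment.

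**Conclusion.** The gap is real but bounded. Infection, transfusion, excessive bleeding as an event, early stops for bleeding or infection, and the reason for each hysterotomy are not planned outcomes. Rupture, blood-loss amount, fever and total hysterotomy are. The planned comparisons cannot show how many women had the missing events, and rupture will probably contribute no events (83.5% chance of none in 60 at 0.3%).

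The omissions follow from the text and need no assumption. The rupture figures take the protocol's 0.3% as applying to both arms. The infection and transfusion probabilities and the power figures use assumed rates. The hysterotomy point depends on how failure is read. The change should be made because safety is a stated aim, but it alters no planned test and no sample size.

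**What to change.** Add to the secondary outcomes, as counts by arm with confidence intervals:

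1. blood transfusion;
2. infection, defined and recorded separately from fever;
3. induction stopped early, for bleeding and for infection separately, with excessive bleeding defined for reporting.

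Count them over the same follow-up period for every woman. If events were counted only during induction, an arm that aborts sooner would be observed for less time.

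Report hysterotomy in two rows, failed induction and complication, with the total kept. The sponsor should clarify in Interventions whether a stop for bleeding or infection counts as failure; no clinical rule is proposed here. The SAP should name these outcomes and label the comparisons descriptive.

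The cost is a few extra data fields and a longer safety table with low counts. The sample size does not change. The SAP is dated February 2020, after the stated study period, so data collection may be over. In that case the items should be sought in whatever records exist, reported as added after the fact, and any that cannot be recovered stated as such.

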Efficacy of Ulipristal Acetate in Induction of Second Trimestric Missed Abortion in Women with Previous Caesarian section: Randomized Controlled Trial.

Document date : February 2020

Statistical analysis:

The collected data were coded, tabulated, and statistically analyzed using IBM SPSS statistics (Statistical Package for Social Sciences) software version 22.0, IBM Corp., Chicago, USA, 2013. Quantitative normally distributed data described as mean±SD (standard deviation) after testing for normality using Shapiro-Wilk test, then compared using independent t-test if normally distributed and Mann Whitney test if not normally distributed, while Pearson test was used for correlations. Qualitative data described as number and percentage and compared using Chi square test and Fisher's Exact test for variables with small expected numbers. Log rank test was used to compare abortion rate. The level of significance was taken at P value < 0.050 was significant, otherwise was non-significant

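### Pain is compared only as occurrence yes/no, so with 30 women per arm a moderate change in its intensity would largely be missed if most women report some pain

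*Protocol*

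**What the plan says.** The protocol (Secondary outcome, item 2) lists "Occurrence of side effects: i) Nausea ii) Vomiting iii) Fever iv) Pain, between both groups". Neither document gives a pain scale, a severity grade, a threshold for counting pain, a time window or an analgesic-use outcome.

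The SAP does not mention pain. A yes/no item falls under its general rule: "Qualitative data described as number and percentage and compared using Chi square test", with Fisher's exact test where expected numbers are small and significance at P < 0.050.

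Both arms receive the same misoprostol (Protocol, Interventions): "Group A: will receive Ulipristal acetate 30mg, starting misoprostol 12 hours later 100µg every 6 hours buccal" and "Group B: will receive placebo tablet then 12 hours later start misoprostol 100µg every 6 hours buccal". Each group has 30 women (Protocol, Randomization, Allocation and Concealment).

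The protocol's background brings in pain through a different drug: "Mifepristone may be used in combination with misoprostol to decrease the induction-to-abortion interval and minimize pain". Its evidence is an amount, "analgesic requirements (27.2 versus 39.3 mg morphine). Side effects were similar between groups", and the same passage calls the difference non-significant. The benefits proposed for ulipristal begin "This may decrease the time taken for patients to abort, may increase the success rate of having a complete abortion" and do not name pain.

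**The concern.** The agent given to cause contractions is common to both arms, and women already contracting are excluded at entry. The useful question is then how much pain each woman has, more than whether she has any. A yes/no item cannot record that. If most controls say yes, a woman whose pain falls from severe to moderate still counts as yes, and so does one whose pain becomes worse.

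The second case matters because the stated aim covers safety as well as effectiveness. The background lists greater uterine sensitivity to prostaglandin among the effects of mifepristone, the drug on which the case for ulipristal is modelled. More pain is therefore a possible result by the same analogy. When the yes rate is already high, it has little room to rise. The comparison would be labelled non-significant under the SAP, and readers may take that as equal pain.

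**Working it through.** **Plan's own figure.** The 30 per group cannot be reproduced. The protocol refers to a pilot of 24 (12 per arm) but gives no effect size, SD, event rate or power. I take n = 30 per arm as fixed.

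**Inputs.** From the documents: n = 30 per arm, significance at P < 0.05, and chi-square or Fisher for qualitative data. Assumed: two-sided tests, Fisher when the smallest expected count is below 5, control pain rates from 50% to 99%, and a normal latent pain score with equal SD in both arms that is recorded as yes above a fixed threshold.

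**Step 1: pain as a score.** For a shift of d SDs, the t-test has noncentrality d × √(n/2) on 58 degrees of freedom.
- d = 0.74: 0.74 × √15 = 2.87, power 80.5%
- d = 0.50: 0.50 × √15 = 1.94, power 48%

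Mann-Whitney on normal data costs little: a simulation of 20,000 trials at d = 0.74 gave 78%.

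**Step 2: the same shift as yes/no.** With control rate p, the other arm's rate is Φ(Φ⁻¹(p) − d) for a fall and Φ(Φ⁻¹(p) + d) for a rise. Example at p = 95%: a fall gives Φ(1.645 − 0.74) = 81.7%, and a rise gives Φ(1.645 + 0.74) = 99.1%. Power is the sum of the binomial probabilities of all tables with P < 0.05 among the 31 × 31 possible.

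| Control rate | Rate after 0.74 SD fall | Power, fall | Rate after 0.74 SD rise | Power, rise |
|---|---|---|---|---|
| 99% | 94.4% | 0.4% | 99.9% | 0.0% |
| 95% | 81.7% | 21% | 99.1% | 0.3% |
| 90% | 70.6% | 45% | 97.8% | 4% |
| 80% | 54.0% | 57% | 94.3% | 25% |
| 50% | 23.0% | 59% | 77.0% | 59% |

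The score has 80% power in every row. For a 0.5 SD fall the score has 48%, and yes/no has 0.0%, 5%, 18%, 29% and 33% at the same control rates. With Fisher throughout, the yes/no powers are the same or lower.

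**Step 3: what yes/no can detect.** With Fisher throughout, 80% power needs a fall of 26 points from 100% (to 74%, power 83%), 27 points from 99% or 31 points from 95%. With the chi-square/Fisher rule the last figure is 29. In counts, if 30/30 controls report pain, 24/30 in the other arm gives P = 0.024 and 25/30 gives P = 0.052.

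**The case against.** Four objections have force.

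- **The rate is unknown.** A reader might infer that pain will sit near 100% in both arms. The documents do not say so. The opioid amounts come from a trial that used misoprostol 400 mcg then 200 mcg every six hours, against 100 µg every 6 hours here. A mean dose does not give the share of women in pain, and the rate depends on an undefined threshold. This stands, so the results above are shown over a range. The loss does not depend on a ceiling: yes/no is worse even at 50% (59% against 80%).
- **Yes/no is not blind.** A reader might infer that it cannot show any reduction. Step 3 shows that a fall of about 26 to 31 points would be detected. A 10-point fall has low power at every control rate tried (7% to 10% by Fisher), so sample size explains part of the weakness. What is lost is information on intensity.
- **Pain is not a stated reason for giving ulipristal.** A reader might infer that it is. The pain sentence concerns mifepristone, the cited morphine difference was non-significant, side effects in that trial were similar, and the research question and hypothesis concern time to abortion. The link is by analogy only.
- **Analgesic dose is a weak substitute.** For the cited difference of 39.3 − 27.2 = 12.1 mg, 30 per arm gives 87%, 63%, 45% and 34% power at assumed SDs of 15, 20, 25 and 30 mg. The first two are optimistic. The quoted retained-placenta rates of 3.1% and 6.3% would fit 1/32 and 2/32. If the arms were about 32 each and the doses are means, non-significance needs an SD above 12.1 / (2.00 × √(2/32)) ≈ 24 mg, hence power below about 48%. Total dose also accumulates with time to abortion, so it partly repeats the primary outcome, and neither document mentions an analgesic or a drug chart. This stands, and the pain score should carry the fix.

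**Conclusion.** The point holds as a limited one. Pain is ungraded, and if most women report some pain, the planned comparison would largely miss a moderate fall in intensity and would miss a rise most often. For a 0.74 SD fall, power drops from 80% as a score to between 0.4% and 57% at control rates of 99% down to 80%. For a rise it is 0.3% at 95% and 4% at 90%.

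These sizes rest on the assumed control rates and the normal latent score. A real 0-10 score is discrete and may bunch near its top, so its advantage could be smaller than shown. The documents do not support saying that pain will be universal, that yes/no can show nothing, or that a stated purpose of ulipristal goes untested. Priority is minor: pain is one secondary safety item, and the primary outcome is unaffected.

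**What to change.** In secondary outcome 2, record worst pain from first tablet to abortion on a 0-10 scale reported by the woman. In the SAP, name Mann-Whitney for this score and report the median difference with its 95% confidence interval. Keep yes/no pain as a descriptive count, with the threshold for yes defined. Where analgesic doses are charted, report the total descriptively and note that it overlaps with time to abortion. State that a non-significant yes/no comparison is not evidence of equal pain.

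The cost is one extra question per woman and one line in each document. The planned study period ended in January 2020 and the SAP is dated February 2020, so scores may no longer be obtainable. In that case, report the yes/no counts with a confidence interval for the difference and state the missing intensity measure as a limitation.

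### Uterine rupture is compared only by a P value that, at 30 per arm, is almost bound to be non-significant; no confidence interval is planned to show the uncertainty

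*Protocol*

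**What the plan says.** The aim opens with safety beside effectiveness: "The aim of this work is to assess the effectiveness and safety of Ulipristal Acetate in the management of 2nd trimester missed abortion". The same sentence ends on time alone: "versus the use of misoprostol only with placebo as regards the time needed for abortion". The Research Question also concerns time only: "does Ulipristal Acetate decrease the time interval to achieve abortion when combined with Misoprostol in comparison to Misoprostol alone". The Hypothesis and the primary outcome follow it.

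Among the secondary outcomes, item 3 is "Rate of uterine rupture between both groups". The eligibility criteria require a previous caesarean scar. On ulipristal acetate (UPA), the background says "It has not been used as an abortifacient drug in previous studies". Allocation is to two groups of 30. The only rupture figure in either document is the 0.3% used for counselling under Ethical Considerations.

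The SAP does not mention rupture. Its rule for qualitative variables is counts with percentages, compared by chi-square, or by Fisher's exact test where expected counts are small. A P value below 0.05 is called significant and anything else non-significant. Neither document mentions a confidence interval for any outcome.

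**The concern.** Counts will be reported, but the P value and its two-way label are the only inference planned for rupture. For an event this rare and arms this small, the label hardly depends on the true rate across a wide range. A table reading 0/30 v 0/30, P = 1, non-significant, looks reassuring while being compatible with rupture rates far above the counselling figure. That matters because UPA is described as untried in this use and every participant has a uterine scar.

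The missing interval affects every outcome. Rupture is singled out because the P value is close to empty there.

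**Working it through.** **Inputs.** From the documents: 30 per arm; significance at P < 0.05; Fisher for small expected counts. With equal arms the expected count per arm is half the total ruptures, so up to 9 ruptures in all it stays below 5 and Fisher is the natural choice. Assumed: a two-sided test (the SAP does not say); a control rate of 0.3% (range 0.1% to 1%); every UPA rupture rate. The plan states no power or precision for rupture, so there is no figure of its own to reproduce.

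**1. What Fisher needs.** With equal arms and k v 0 ruptures, two-sided P = 2 × C(30,k) / C(60,k).
- 5 v 0: 2 × 142,506 / 5,461,512 = 0.052
- 6 v 0: 2 × 593,775 / 50,063,860 = 0.024
- With one control rupture: 7 v 1 gives 0.052 and 8 v 1 gives 0.026.

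So the smallest significant excess is 6 v 0, or 20% of the UPA arm.

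**2. Chance of a significant result.** Sum Bin(a; 30, p_UPA) × Bin(b; 30, p_control) over all 31 × 31 tables with Fisher P < 0.05.

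| Assumed UPA rate | Power, control 0.3% | Control 1% to 0.1% |
|---|---|---|
| 3% | 0.02% | 0.02% to 0.02% |
| 5% | 0.30% | 0.24% to 0.32% |
| 10% | 6.8% | 5.6% to 7.1% |
| 15% | 27% | 23% to 28% |
| 20% | 54% | 48% to 56% |

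The chance of non-significance is 100% minus this: about 99.7% at 5%, about 93% at 10% and 73% at 15%. Cross-check at 5% with no control ruptures: P(6 or more of 30) = 0.33%.

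**3. The likeliest result.** P(0 v 0) = (1 − p_UPA)^30 × (1 − p_control)^30.
- 0.3% in both arms: 0.997^60 = 83.5%
- UPA 3%, control 0.3%: 0.97^30 × 0.997^30 = 37%
- UPA 5%, control 0.3%: 0.95^30 × 0.997^30 = 20%

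At 0 v 0 chi-square is undefined, and Fisher returns P = 1 because only one table is possible.

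**4. What an interval would show.** These limits need no assumed rate.
- Clopper-Pearson, 0/30: upper limit 1 − 0.025^(1/30) = 11.6%, about 39 times 0.3% (11.6 / 0.3). For 1/30: 0.1% to 17.2%.
- Newcombe difference (UPA minus control), built from the Wilson limits of each arm. At 0/30 the Wilson upper limit is z²/(30 + z²) = 3.84/33.84 = 11.35%, so 0 v 0 gives −11.4 to +11.4 points. 1 v 0 gives −8.3 to +16.7; 2 v 0 gives −5.7 to +21.3.

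**5. Sensitivity to the test.** If uncorrected chi-square were used despite small counts (the SAP does not define small), 4 v 0 would suffice (P = 0.038). Power would be 1.1%, 5.6% and 33% at UPA rates of 3%, 5% and 10%.

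**The case against.** The strongest reply is that nothing in the plan is contradicted. Rupture is one of five secondary outcomes, the research question and primary outcome concern time, and nothing says that 30 per arm was chosen for rupture. Almost any 60-patient trial is uninformative on a rare event. The counts will be published, so a reader can derive the 11.6% limit unaided. All of this stands, and it makes the point an improvement in reporting rather than an error that damages the main result.

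A reader might infer more than the documents support:
- *That the trial intends to declare rupture risk equal.* No equivalence or non-inferiority claim is planned. The SAP simply gives no guidance on how to read a non-significant result.
- *That the test is blind whatever the truth.* The near-certainty depends on Fisher, a low control rate and a UPA rate up to about 5%. At a control rate of 8%, non-significance can fall to 97.1% within that UPA range. At a UPA rate of 15% or more the near-certainty is gone. The 5% ceiling is an illustration, not a figure from the documents.
- *That the P value should be discarded.* A 6 v 0 split (P = 0.024) would be an informative signal of harm. Barring the P value would lose it, and would change the decision rule after the stated study period.

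An interval also does not create power. With a 0.3% control rate, the Newcombe interval excludes zero with probability 0.17% at a UPA rate of 3% and 1.4% at 5%. Its gain is that the uncertainty becomes visible.

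**Conclusion.** The point holds as a limited, low-cost improvement. The only planned inference for rupture is a label that is non-significant with about 99.7% probability at a UPA rate of 5% and about 93% at 10%, given two-sided Fisher, 30 per arm and a 0.3% control rate. Sidedness and all rates are assumptions; the 11.6% upper limit for 0/30 depends on none of them. The primary result is unaffected. What changes is what the report can honestly say about rupture.

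**What to change.** Add to the SAP:

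> Uterine rupture will be reported as number/total per arm with exact (Clopper-Pearson) 95% confidence intervals, and as a between-group risk difference with a Newcombe 95% confidence interval, alongside the planned Fisher P value. Neither zero ruptures nor a non-significant P value will be taken as evidence of equal or acceptable rupture risk.

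Use the actual denominators, and keep the P value. The protocol gives the study period as "Starting from January 2019 to January 2020" and the SAP carries "Document date : February 2020", so if rupture has already been analysed, mark the text as a later addition.

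The cost is two sentences, with no new data or patients. There are two downsides. The statement on rupture becomes more modest. The interval and Fisher can also disagree near the margin: 5 v 0 gives Newcombe +2.0 to +33.6 points with P = 0.052, and 7 v 1 gives +2.4 to +37.8 points with P = 0.052. In such cases report both.
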